9 CLINICAL MANAGEMENT

There are no additional clinical management considerations for participants enrolled in this study. Participants who express concerns with social, psychological or clinical issues will receive appropriate care and counseling to the extent possible, and/or be referred for appropriate care to services available at the CRS, or at nearby partnering facilities.

9.1 Criteria for Early Termination of Study Participation

Participants may voluntarily withdraw from the study for any reason at any time. The IoR also may withdraw participants from the study to protect their safety and/or if they are unwilling or unable to comply with required study procedures. Participants also may be withdrawn if the study sponsors, government or regulatory authorities, including the Office for Human Research Protections (OHRP), or site IRBs/ECs terminate the study prior to its planned end date. Study staff members will record the reason(s) for all withdrawals in participants' study records. In the event that participants who voluntarily withdraw from the study wish to re-join the study, they may do so if the accrual target has not yet been met.

10 ANALYTICAL CONSIDERATIONS

10.1 Overview and Summary of Design

MTN-045 is a cross-sectional study that will utilize questionnaires, including DCEs and joint decision tasks, and IDIs to assess heterosexual couples' preferences related to DPP products that could be used to prevent unintended pregnancies and HIV infection.

One main goal of the study is to determine heterosexual couples' preferences for a DPP product to inform product delivery and future product design to maximize uptake and willingness to use among sub-Saharan African heterosexual couples. Another main goal of the study is to assess the level of influence of the male partner on a woman's preferences for a DPP product and on her decision-making process regarding product preferences and use.

Secondary objectives of the study include:

- To identify factors that may influence DPP product interest and preferences in heterosexual men, women and couples, including individual and relationship characteristics, and product "positioning" (i.e., contraceptive+HIV prevention vs. HIV prevention+contraceptive).
- To examine differences in preferences and individual vs. joint decision-making by several sociodemographic factors, including age of the woman (e.g., 18-24 vs. 25-40) and parity (nulliparous vs. parous).

10.2 Study Endpoints

The study will examine DPP product preferences of heterosexual couples in SSA. Survey questionnaires will be conducted with each enrolled participant, first separately from their partner and then in conjunction with their partner. In particular, the survey questionnaires will focus on the following primary and secondary endpoints:

- Attributes of a DPP product that influence preferences among heterosexual couples.
- Differences in DPP product attribute preferences when comparing individual to couples' choices (e.g., woman's individual preferences vs. preferences indicated through the joint couples decision task).
- Salient relationship-based and decision-making factors that influence DPP product interest and preferences.
- Differences in attributes salient to preferences by sociodemographic factors such as age and parity that may reflect lifecourse stage.

A single IDI will also be conducted with a subset of up to 80 participants (i.e., one or both partners from up to 40 couples) enrolled in the study in order to gain additional insight on their responses to the survey questionnaire topics above. This IDI will explore participants' interest in and preferences for a DPP product, relevant challenges and facilitators of prior contraceptive and/or HIV prevention product use, social and relationship dynamics that influence decision-making, and any recommendations for future product implementation.

10.3 Sample Size and Composition

The study will enroll approximately 400 heterosexual couples across the study sites. Women who are currently using contraceptives as well as those not using contraceptives will be eligible. Couples who are living together as well as those not living together will be eligible. Community-based recruitment will be conducted through stakeholder engagement with consultation from CAB members. Participants will complete survey questionnaires, first separately from their partner, then followed by a joint couples' decision task. Up to 80 participants, i.e., one or both partners from a subset of up to 40 couples, will be selected to complete an IDI.

10.4 Data and Study Monitoring Procedures

Demographic and behavioral data will be captured electronically on tablet computers. Qualitative data will be audio-recorded, translated and transcribed in English, and coded for thematic analyses using Dedoose or a similar qualitative software. RTI International will function as the overall data coordinating center for quantitative and qualitative data and will lead all analyses.

No Study Monitoring Committee (SMC) review will be performed for MTN-045 given the non-clinical nature of the study. Protocol team members from the MTN, including RTI International and FHI 360, will provide oversight of study operations and ensure the study is implemented in accordance with MTN standards, as defined in the MTN Manual of Operating Procedures.

10.5 Data Analysis

10.5.1 Quantitative analysis – Primary endpoints

A random parameters logit (RPL) model will be used to estimate preferences for the attributes of a DPP product. The model will include a parameter for the couple to account for the clustered structure of the data. The preference weight estimates from the RPL model will be used to estimate which attribute of a DPP was most influential on participants' product choice.

The level of discordance between the woman's individual preference and the couple's preference will be described by counts and frequencies. A regression model will be used to estimate congruency between the woman's individual preference and the couple's joint preferences, by using the woman's preference to predict the joint preference.

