3 OBJECTIVES

3.1 Primary Objectives

- To determine heterosexual couples' preferences for a DPP product to inform product delivery and future product design to maximize uptake and willingness to use among sub-Saharan African heterosexual couples.
- To assess the level of influence of the male partner on a woman's preferences for a DPP product and on her decision-making process regarding product preferences and use.

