7 STUDY PROCEDURES

7.1 Study Visits

Approximately 400 couples will be enrolled (see [Section 10.3](#) for sample composition details). Participants may be screened either separately or together with their partner, and site staff may explain the study to participants either separately or together with their partner, but other key components of participants' consent will be solicited separately to reduce the potential for participant coercion (see [Section 13.5](#) for additional details).

Survey questionnaires will be administered to each member of the couple separately. The individual questionnaires will be followed by a joint couple decision task completed by the couple together. Prior to completing the questionnaires, enrolled participants will receive an introduction to DPP products using standardized materials.

A subset of up to 80 participants (i.e., one or both partners from up to 40 couples) will be selected to complete a single post-survey explanatory IDI to provide further insight on the participants' survey responses and on any unexpected and/or interesting examples of experiences and behaviors relevant to the study endpoints.

Study visits may take place at the study clinic, at the participant's home, or at any other location agreed upon by the participant(s) and the study staff. Multiple visits may be conducted to complete all required procedures, if necessary.

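### The primary analysis of male influence compares only the woman with the couple, so a departure from her choice cannot be attributed to the man

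*Protocol*

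**What the plan says.** Protocol section 3.1 sets as a primary objective "To assess the level of influence of the male partner on a woman's preferences for a DPP product and on her decision-making process". Section 10.2 lists the matching endpoint as "Differences in DPP product attribute preferences when comparing individual to couples' choices", with woman versus joint task given as an example.

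Section 10.5.1 names two analyses for this endpoint:
- Descriptive: "The level of discordance between the woman's individual preference and the couple's preference will be described by counts and frequencies".
- Model: "A regression model will be used to estimate congruency between the woman's individual preference and the couple's joint preferences", which is to be done "by using the woman's preference to predict the joint preference".

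No other predictor is named. The man's data exist. Section 7.1 states: "Survey questionnaires will be administered to each member of the couple separately", and the joint task follows. Section 10.3 gives the size: "The study will enroll approximately 400 heterosexual couples across the study sites".

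**The concern.** Three things determine woman-couple agreement: how alike the partners already were, how much weight each had when they differed, and how consistently people answer twice. The woman-couple comparison yields one number and cannot separate them. High agreement may mean that her view prevailed, or that his prevailed and was the same as hers. Low agreement may mean that he moved the choice, or only that her answers are unstable.

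At stake is the interpretation of a primary objective. The study could be run exactly as written and report a precise congruency estimate that fits both no male influence and complete male control.

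**Working it through.** The protocol gives no figure on this point to reproduce, so the check is one of identification. All values of a, w, e, ρ, k and σ² below are assumptions.

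**Binary model.** Let a be the share of couples whose private choices agree, w the share of disagreements in which the joint choice follows the man, and e the share of joint choices that flip by chance. Then:
- Woman-couple agreement: C = (1−e)[1−(1−a)w] + e(1−a)w.
- Share of disagreements that go the man's way: S = w(1−e) + (1−w)e.
- With choices coded ±1, the expected joint choice is (1−2e)[(1−w)·woman + w·man]. The two-predictor coefficients are therefore (1−2e)(1−w) for her and (1−2e)w for him. His share of the total weight is w, whatever e is.

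| a | w | e | C | her weight | his weight | S |
|---|---|---|---|---|---|---|
| 0.2 | 0.25 | 0 | 0.80 | 0.75 | 0.25 | 0.25 |
| 0.6 | 0.50 | 0 | 0.80 | 0.50 | 0.50 | 0.50 |
| 0.8 | 1.00 | 0 | 0.80 | 0 | 1.00 | 1.00 |
| any | 0 | 0.2 | 0.80 | 0.60 | 0 | 0.20 |

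With balanced choices, the log-odds coefficient in a woman-only logistic regression is 2·ln(0.80/0.20) = 2.77 in every row. Simulation of 400 couples gave 2.78, 2.79, 2.77 and 2.80 for the four rows in order. In the noise-only row, the man's coefficient in a two-predictor logistic model was about 0 (−0.001).

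**Precision is not the problem.** At C = 0.80 and 400 couples the 95% half-width is 1.96·√(0.8·0.2/400) = 0.039.

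**Ordering can reverse.** Take a latent-normal model: joint = k·woman + (1−k)·man + error, partner correlation ρ, error variance σ². Then r = [k+(1−k)ρ]/√(k²+(1−k)²+2k(1−k)ρ+σ²), and agreement = 1/2 + arcsin(r)/π.
- Man decides everything, ρ = 0.7, σ² = 0.25: r = 0.7/√1.25 = 0.626, agreement 71.5%.
- Equal weight, ρ = 0, σ² = 0.25: r = 0.5/√0.75 = 0.577, agreement 69.6%.
- Woman decides everything, σ² = 0.25: r = 1/√1.25 = 0.894, agreement 85.2% for any ρ.

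The first two cases show slightly more woman-couple agreement under full male control than under equal weight.

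**Limit of the disagreement share.** S is not zero when male influence is zero. The last table row gives 0.20, the same as w = 0.20 without noise. In the latent model with the woman deciding and σ² = 0.25, S is 1 − 0.852 = 0.148 at ρ = 0 and about 0.23 at ρ = 0.7 (simulated). With more noise (woman-joint correlation 0.7) it is about 0.25 and 0.33. S therefore cannot lead on its own.

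**Precision of S** near 0.5 is 1.96·√(0.25/n): 0.069 with 200 discordant couples, 0.11 with 80, 0.155 with 40.

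**The case against.** Four points on the other side carry weight.

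1. A reader might infer that the protocol restricts the regression to the woman's preference. It names no other predictor, but it does not exclude one, and a study analysis plan not among the documents reviewed could add the man's. The point survives because the protocol itself fixes the contrast, outcome and predictor for a primary objective, and these do not fit that objective.

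2. A reader might infer that the planned analyses say nothing about male influence, or will give the opposite of the truth. The documents do not support that. Section 10.5.1 calls the regression an estimate of congruency and gives no rule for turning it into influence. If influence means realised change in her choice once he is present, woman-couple departure is relevant. What it cannot do is attribute the departure to him rather than to noise, or show decision weight where the partners already agreed.

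3. Other parts of the plan bear on the man's role: an exploratory endpoint on individual versus couple choices, relationship-factor interactions in section 10.5.2, and interviews with up to 80 participants. None puts his choice into the primary influence analysis.

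4. Section 7.2.1 describes individual choices between product pairs, but a joint task about attribute likes and dislikes. A simple count of who won assumes matched scales and two possible outcomes, which is not established. This limits the remedy, not the concern.

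**Conclusion.** The point holds as one of attribution. Section 10.5.1 describes how far the couple's choice departs from the woman's private choice. Without the man's preference, it cannot say how much of that departure is his doing.

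The size is illustrative: under the assumed models, one agreement figure of 80% covers everything from no male influence to complete male control. The correlations, noise levels and discordance rates are not in the documents. The logical point needs only that partners may be alike and that answers may vary.

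The two-predictor model is better but not perfect. Its weights cannot be separated if partners almost always agree or almost always differ. Noise in her private answers could also pass some weight to him when the partners are alike.

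**What to change.** In section 10.5.1:
- Enter both partners' individual preferences as predictors of the joint preference. Report the man's weight beside the woman's, each with a 95% CI, as the main influence measure. The planned regression already needs her preference in a usable form, and his can be built the same way.
- Report man-versus-couple discordance beside woman-versus-couple discordance. The endpoint wording in section 10.2 already allows this.
- Where individual and joint responses are on the same scale, report as supportive only the outcome among couples whose private preferences differ: man's favour, woman's favour, or neither. Note that choice noise alone makes the man's share non-zero.
- State that woman-couple discordance alone is not interpreted as male influence.

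The cost is protocol and analysis-plan wording and a little more analysis. His individual preferences are already collected. The precision of the added estimates will depend on how many couples disagree, which is not known in advance.

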10.5.2 Quantitative analysis – Secondary endpoints

To explore differences in preferences by relationship-based indicators and sociodemographic factors (such as age and parity), separate random parameter logit models will be estimated with interaction terms between the factors of interest and attribute levels. Additional methods, such as latent class analysis, may be used to explore preference heterogeneity by identifying sub-groups defined by distinct sociodemographic, behavioral and relationship-based characteristics with varying preferences. The study analysis plan will explain the application of these analytic approaches in greater detail.

10.5.3 Qualitative analysis

Data Sources

The qualitative data from MTN-045 will include three main data sources:

- Original handwritten interview notes and observation checklists (questionnaires and IDIs)
- Audio-recorded IDIs
- Transcripts of IDIs

Qualitative data will be audio-recorded, translated and transcribed in English, and coded for thematic analyses using Dedoose or a similar qualitative software.

Qualitative Analysis Overview

The following section provides a brief overview of the analysis process; however, a more detailed description of the qualitative analysis will be presented in the study analysis plan.

Qualitative analyses from the MTN-045 study will use a variety of techniques to provide an in-depth characterization of the contextual factors that affected participants' DPP product preferences. The primary source of qualitative data used in the MTN-045 analysis will consist of raw textual data. Qualitative data will be audio-recorded, translated and transcribed in English, and coded for thematic analyses using Dedoose or a similar qualitative software. Data coding will be used as a primary analytical approach for data reduction; that is, to summarize, extract meaning, and condense the data.^{121,122} MTN-045 transcripts will be coded first through descriptive coding for key themes and topics, using a preliminary codebook (see [Section 10.5.4](#)).¹²³ Additional codes will be identified through an iterative process of reading the textual data to identify emergent themes, and the codebook will be modified accordingly. In addition to descriptive codes, pattern codes, which achieve a greater level of abstraction, will be used to start linking themes and topics together in order to explore the relationship between socio-contextual factors and product preferences, as well as between product attributes and preferences.¹²¹ Whenever possible, we will also compare study sites and explore differences or similarities related to product preferences due to different socioeconomic, cultural and geographical contexts. The analysis will be done by the investigative team, working interactively through emails, and regular phone or face-to-face meetings. The findings and interpretations of the data will be critically discussed until there is group consensus on the dominant themes and meanings contained in the data.¹²⁴ Whenever possible, site staff will be involved to corroborate findings from the analysis team.

10.5.4 Codebook Development and Coding Process¹²⁵

Coding is an essential process for data reduction necessary for the management and interpretation of large amounts of qualitative data. Staff at RTI International will develop a codebook and study procedures for coding and analysis of all of the qualitative data. Each code will be operationally-defined and refined in an iterative way, as needed. Transcripts will be coded using a qualitative software package such as Dedoose.

During the study development stage, a set of preliminary codes will be developed based on the research questions of this study. The analysis coding structure will be hierarchical, and will reflect the topics/themes covered in the interview guides. After the first 2-3 interviews are completed, each member (analyst) of the coding group will apply this initial set of thematic codes to a common transcript, discuss their coding experiences (via email, a meeting, or conference call), and agree on expanding and modifying code names and definitions when necessary. The coding team will generate substantive and conceptual categories through an iterative process of reading the data, and generating codes based on the data and on key themes or topics identified *a priori*, applying the codes to the data, and refining these as coding progresses. Thus, codes will be centered on the main topics of interest (e.g., product preferences: product attributes influencing product initiation, persistence and implementation, and environmental challenges and facilitators of product use) and the hypothesized contextual spheres of influence. However, by nature, the qualitative research process is iterative, and the Dedoose software allows for the generation of new codes for emergent themes that were not identified *a priori* by the research team. The software also allows for coders to insert descriptive comments and memos to themselves and others as they are working, and to code for concepts not spelled out in verbatim text, such as "contradiction," when a participant contradicts herself.

Once finalized, the codebook will be used for coding of all of the transcripts. Comprehensive listings of all coded quotations for every code (as well as “families” of related codes) will be generated in Dedoose. The coding team will consider the coded dataset in its entirety, and “stratify” the coded quotations by factors such as the site, relationship dynamics, reported opinions of preferred product attributes, or reported opinions of environmental challenges and facilitators of product use. These stratifications will depend on findings from the analysis of these data clusters.

The coding process will involve a core group of at least 2-3 analysts who will frequently communicate (via email, phone or in person meetings) and discuss their use of the codebook and application of the codes during the coding process. Inter-rater reliability will be assessed among all coders on a pre-selected proportion of transcripts via use of Dedoose or other coding software tests. Following this process, the coding team will discuss (in person or via teleconference) the coding discrepancies, which will ultimately be resolved through consensus. Regular discussions among the coding team will ensure that coding remains standardized and reliable.

11 DATA HANDLING AND RECORDKEEPING

11.1 Data Management Responsibilities

Study data will be collected electronically on password-protected tablet computers. Interview data will be digitally transferred to a secure electronic database. Data will be routinely backed up to a server housed by RTI International, where all electronic data will be stored on secure, password-protected computers accessible by key study personnel only. Quality control (QC) reports and queries routinely will be generated and distributed by RTI International to the study sites for verification and resolution. As part of the study activation process, each study site must identify all electronic interview files to be used as source documents.

IDI guides will be developed by RTI International in conjunction with the protocol team and, where required, will receive IRB/EC approval. Source documents include audio files, transcripts, observation checklists and interview notes. Transcripts of IDIs will be generated using the audio recordings. The transcripts will be electronically transferred to RTI International using a secure File Transfer Protocol (FTP) site, where they will be uploaded and analyzed using a qualitative software package. Interview audio files, observation checklists and notes will be kept at the site in the participant files. RTI International will act as a hub, and manage all data for the study. A convention for file naming will be developed, and all data will be labeled according to this process. Transcripts will be transferred to RTI International as they are completed. RTI International will save all versions of all files on a secure, password-protected server.

11.2 Source Documents and Access to Source Data/Documents

All study sites will maintain source data/documents in accordance with Requirements for Source Documentation in DAIDS Funded and/or Sponsored Clinical Trials (<https://www.niaid.nih.gov/sites/default/files/daids-sourcedocpolicy.pdf>) and the relevant appendix regarding source documentation (<https://www.niaid.nih.gov/sites/default/files/sourcedocappndx.pdf>).

For MTN-045, source documentation may include recruitment logs, enrollment records, visit checklists, paper CRFs, electronic interview data, participant file notes, and electronic audio files. Essential documentation for the study also includes all versions of the protocol, informed consent forms, operating procedures and key communication with the protocol team. In accordance with U.S regulations, each IoR/designee will maintain, and store securely, complete, accurate and current study records throughout the study.

Study records must be maintained on site for the entire period of study implementation. Thereafter, instructions for record storage will be provided by DAIDS. No study records may be moved to an off-site location or destroyed prior to receiving approval from DAIDS.

